5.4 Removal of Subjects from Therapy or Assessment

5.4.1 Discontinuation of Individual Subjects

Each subject has the right to withdraw from treatment or the study at any time. In addition, the investigator may discontinue a subject from treatment or the study at any time if the investigator considers it necessary for any reason, including the occurrence of an adverse event or noncompliance with the protocol.

If, during the course of study drug administration, the subject prematurely discontinues treatment, the procedures outlined for the applicable Premature D/C Visit should be completed as defined in [Table 4](#). It is recommended that this visit occur on the day of study drug discontinuation; however, this visit should occur within 2 days following their final dose of study drugs and prior to the initiation of any other anti-HCV therapy. However, these procedures should not interfere with the initiation of any new treatments or therapeutic modalities that the investigator feels are necessary to treat the subject's conditions. Following discontinuation of study drugs, the subject will be treated in accordance with the investigator's best clinical judgment. The date of the last dose of study drug and reason for discontinuation will be recorded in the eCRF. The subject should then begin the PT Period where the subject will be monitored for 48 weeks for safety, HCV RNA, the emergence and persistence of resistant viral variants, and assessments of PROs.

If a subject discontinues from the PT Period, the subject should return for post-treatment discontinuation procedures defined in [Table 5](#). The reason for discontinuation will also be recorded in the eCRF.

If a subject is discontinued from study drug (Treatment Period) or the PT Period with an ongoing adverse event or an unresolved laboratory result that is significantly outside the reference range, the investigator will attempt to provide follow-up until a satisfactory clinical resolution of the laboratory result or adverse event is achieved (Section [6.7](#)).

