5.4.1.1 Virologic Failure Criteria for Subject Management

The following criteria will be considered evidence of virologic failure leading to discontinuation of study drug while receiving study drug and will be discontinued from study drug:

- Confirmed increase from nadir in HCV RNA (defined as 2 consecutive HCV RNA measurements of $> 1 \log_{10}$ IU/mL above nadir) at any time point during treatment; or
- Failure to achieve HCV RNA $<$ LLOQ by Week 8; or
- Confirmed HCV RNA \geq LLOQ (defined as 2 consecutive HCV RNA measurements \geq LLOQ) at any point during treatment after HCV RNA \leq LLOQ.

Confirmatory testing should be completed as soon as possible. Subjects should remain on study drug treatment until the virologic failure has been confirmed. If any of the above criteria are met, the subject will discontinue study drug treatment (Section [5.4.1](#)).

Subjects with HCV RNA < LLOQ at the end of treatment and who have a confirmed HCV RNA \geq LLOQ (defined as 2 consecutive HCV RNA measurements \geq LLOQ) at any point in the PT Period will be considered to have relapsed. Confirmation of an HCV RNA \geq LLOQ in the PT Period should be completed as soon as possible per Section [5.1.3](#).

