Note: Data must also have Study Drug End Day ≤ 2 for all windows. The result closest to the scheduled time point will be used. Child-Pugh classification (for cirrhotic subjects only), FibroTest are collected at Screening and Week 12 (or upon study discontinuation) and will use those visit windows as defined above. FibroTest is also collected at baseline, only if not performed at the time of screening.

Table 3. Analysis Time Windows for HCV RNA, Resistance Endpoints, Laboratory Data, and Vital Sign (Treatment Period) for 8-Week of Treatment

Scheduled Visit	Nominal Day (Study Day)	Time Window (Study Day Range)
Day 1/Baseline ^a	1 ^a	≤ 1 ^a
Week 1	7	2 to 10
Week 2	14	11 to 21
Week 4	28	22 to 42
Week 8	56	43 to 70
Final Treatment Visit ^b		2 to ≤ 2 days after last dose of study drug

a. Day of first dose of study drug.

b. The last value within the window will be used to define the Final Treatment visit value. The upper bound of this Final window is Study Drug End Day ≤ 2.

Note: Data must also have Study Drug End Day ≤ 2 for all windows. The result closest to the scheduled time point will be used.

Table 4. Analysis Time Windows for HCV RNA, Resistance Endpoints, Laboratory Data, and Vital Sign (Treatment Period) for 6-Week of Treatment

Scheduled Visit	Nominal Day (Study Day)	Time Window (Study Day Range)
Day 1/Baseline ^a	1 ^a	≤ 1 ^a
Week 1	7	2 to 10
Week 2	14	11 to 21
Week 4	28	22 to 35
Week 6	42	36 to 49
Final Treatment Visit ^b		2 to ≤ 2 days after last dose of study drug

a. Day of first dose of study drug.

b. The last value within the window will be used to define the Final Treatment visit value. The upper bound of this Final window is Study Drug End Day ≤ 2.

Note: Data must also have Study Drug End Day ≤ 2 for all windows. The result closest to the scheduled time point will be used.

Table 5. Analysis Time Windows for HCV RNA, Resistance Endpoints, (Post-Treatment Period)

Scheduled Visit ^a	Nominal Day (Study Drug End Day)	Time Window (Study Drug End Day Range)
Post-Treatment Week 2	14	3 to 21
Post-Treatment Week 4	28	22 to 42
Post-Treatment Week 8	56	43 to 77
Post-Treatment Week 12	84	78 to 126
Post-Treatment Week 24	168	127 to 210
Post-Treatment Week 36	252	211 to 294
Post-Treatment Week 48	336	295 to 378
SVR ₄ ^b	28	3 to 56
SVR ₁₂ ^b	84	57 to 126
SVR ₂₄ ^b	168	127 to 210

a. Post-Treatment Visits are applicable for subjects who received at least one dose of study drug.

b. For SVR windows, the last value in the window will be used.

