EOTR (end of treatment response) = HCV RNA < LLOQ in the Week 12 window for 12-week regimen, Week 8 window for 8-week regimen, and Week 6 for 6-week regimen.

SVR₄ = HCV RNA < LLOQ in the SVR₄ window (4 weeks after the last actual dose of study drug) without any confirmed quantifiable (\geq LLOQ) post-treatment value before or during that SVR window.

SVR₁₂ = HCV RNA < LLOQ in the SVR₁₂ window (12 weeks after the last actual dose of study drug) without any confirmed quantifiable (\geq LLOQ) post-treatment value before or during that SVR window.

SVR₂₄ = HCV RNA < LLOQ in the SVR₂₄ window (24 weeks after the last actual dose of study drug) without any confirmed quantifiable (\geq LLOQ) post-treatment value before or during that SVR window.

Relapse₁₂ = confirmed HCV RNA \geq LLOQ between end of treatment and 12 weeks after last actual dose of active study drug (up to and including the SVR₁₂ assessment time point) for a subject with HCV RNA < LLOQ at Final Treatment Visit who completes treatment, excluding re-infection as described below.

Relapse₂₄ = confirmed HCV RNA \geq LLOQ during SVR₂₄ window among subjects who achieved SVR₁₂ and have data available during the SVR₂₄ window, excluding re-infection.

Relapse_{late} = confirmed HCV RNA \geq LLOQ at any time after the SVR₂₄ assessment time point for a subject who achieved SVR₂₄ and has post-SVR₂₄ HCV RNA data available, excluding re-infection.

Relapse_{overall} = confirmed HCV RNA \geq LLOQ between end of treatment and up to and including the last HCV RNA measurement collected in the PT Period for a subject with HCV RNA < LLOQ at Final Treatment Visit who completes treatment. Completion of treatment is defined as a study drug duration \geq 37 days, \geq 49 days and \geq 77 days for planned treatment duration of 6 week, 8 weeks and 12 week, respectively. Also, include a

summary of Relapse_{overall} for subjects who prematurely discontinued treatment, excluding re-infection.

For relapse analyses, the completion of treatment is defined as above. If the last available post-treatment value is \geq LLOQ, then the subject will be considered a relapse (i.e., will not require confirmation). Relapse analyses will exclude subjects who do not have any post-treatment HCV RNA values.

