10.6 Additional Efficacy Analyses

The following additional efficacy endpoints will be summarized and analyzed for each treatment arm:

- All reasons for not achieving SVR₁₂ for subjects who do not achieve SVR₁₂;
- Number and percentage with unquantifiable HCV RNA at each post-baseline visit throughout the Treatment Period (using data from the central laboratory as observed, i.e., no imputation for missing data);
- The percentage of subjects with HCV RNA < LLOQ 24 weeks after the last actual dose of study drug (SVR₂₄);
- All reasons for not achieving SVR₂₄ for subjects who do not achieve SVR₂₄.
- Time to suppression of HCV RNA (defined as the study day of the first of two successive HCV RNA < LLOQ) during the Treatment Period.

In the above analyses that use the number and percentage of responders, the rates and 2-sided 95% Wilson score confidence interval for a binomial proportion will be calculated.

For HCV RNA levels, the time to suppression during treatment will be calculated for each subject, and the median time will be estimated using Kaplan-Meier methodology for right censored observations.

Imputations for missing data will be performed as described in Section 6.3 for analyses of SVR, RVR, and EOTR where a missing response will be imputed as a failure after performing the described imputation. All other endpoints will be presented using data as observed.

The number and percent of subjects who fail to suppress HCV RNA and received at least 6 weeks of treatment (active study drug duration \geq 38 days) will be tabulated along with the subject numbers corresponding to the subjects who failed to suppress.

The number of subjects who breakthrough at any time during treatment and within each protocol-specified visit (defined in [Table 2](#), [Table 3](#), and [Table 4](#)) will be summarized along with a corresponding listing displaying the subject numbers at the first occurrence of breakthrough.

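### The by-visit percentage with unquantifiable HCV RNA uses observed values only, so any stop for virologic failure biases the later treatment visits upward, chiefly Week 12 in the 12-week arms

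*SAP*

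**What the plan says.** **The summary.** SAP 10.6 lists, for each arm, the number and percentage with unquantifiable HCV RNA at every post-baseline treatment visit, "using data from the central laboratory as observed, i.e., no imputation for missing data". Protocol 8.1.2.3 has the same rule. Both sections attach two-sided 95% Wilson intervals to responder percentages.

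**The stopping rule.** Protocol 5.4.1.1 defines virologic failure as not reaching HCV RNA below LLOQ by Week 8, a confirmed return to LLOQ or above after suppression, or a confirmed rise of more than 1 log10 from nadir. It then says "If any of the above criteria are met, the subject will discontinue study drug treatment". Before that, "Subjects should remain on study drug treatment until the virologic failure has been confirmed". Under Protocol 5.4.1 a stopped subject has a discontinuation visit, and "this visit should occur within 2 days following their final dose of study drugs". Protocol Table 4 includes an HCV RNA sample at that visit.

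**The windows.** For the 12-week arms, SAP Table 2 sets Week 8 as Study Days 43 to 63, Week 10 as Days 64 to 77 and Week 12 as Days 78 to 98. Its note adds: "Data must also have Study Drug End Day ≤ 2 for all windows".

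**The neighbouring endpoint.** SAP 10.1 defines "EOTR (end of treatment response) = HCV RNA < LLOQ in the Week 12 window for 12-week regimen". SAP 10.6 handles SVR, RVR and EOTR differently from the by-visit percentage, in a rule "where a missing response will be imputed as a failure after performing the described imputation".

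**The concern.** The values are missing because of the outcome being summarised. A subject who is quantifiable is taken off drug. Later samples are post-treatment by definition and cannot enter a treatment window, so the failure disappears from numerator and denominator together. The remaining subjects have been selected partly for being suppressed.

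The by-visit percentage is one of the trial's descriptions of on-treatment antiviral activity, and Protocol 5.6.1 says the study should inform on the role of ribavirin. With about 10 subjects per arm, one or two lost failures can turn a visible shortfall into 100%, with a Wilson interval shifted upward to match. The same report could also carry two Week 12 suppression rates for one arm, from one window, that differ only in how a stopped subject is counted.

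**Working it through.** **Check of the interval method.** The Wilson formula gives 59.6% to 98.2% for 9/10 and 69.9% to 97.2% for 18/20. Both match SAP 4.3. The documents state no figure for the by-visit percentage itself.

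**Which windows a stop empties.** Study Drug End Day 0 is the day of the last dose (SAP 6.1.2), and a treatment-window value needs End Day 2 or less.

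- Week 12 opens on Day 78. With a last dose on or before Day 75, Day 78 is End Day 3 or later (78 − 75 = 3), so the window can hold no value.
- Week 10 opens on Day 64. With a last dose on or before Day 61, Day 64 is End Day 3 or later (64 − 61 = 3), so the window can hold no value.
- If the discontinuation sample is drawn on Days 64 to 77 and within 2 days of the last dose, it is an admissible Week 10 value. A subject quantifiable at Day 56 who has this sample 8 to 21 days later (64 − 56 = 8; 77 − 56 = 21) can therefore count as not suppressed at Week 10. Week 12 is still empty for that subject if the last dose was on or before Day 75.

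**Size of the bias.** Let n be the arm size, s the number stopped for virologic failure with no value in the window, and x the number suppressed in it. Assume no other values are missing.

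- As observed: x/(n − s).
- Stopped subjects kept as not below LLOQ: x/n.
- Difference: x·s / [n(n − s)], which is zero when s = 0 and equals s/n when all remaining subjects are suppressed (x = n − s).

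The documents give no expected number of stops, so s is varied from 0 to 3, with all remaining subjects suppressed:

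| n | s | As observed (Wilson 95%) | Stops counted (Wilson 95%) |
|---|---|---|---|
| 10 | 0 | 10/10 = 100% (72.2–100) | 10/10 = 100% (72.2–100) |
| 10 | 1 | 9/9 = 100% (70.1–100) | 9/10 = 90% (59.6–98.2) |
| 10 | 2 | 8/8 = 100% (67.6–100) | 8/10 = 80% (49.0–94.3) |
| 10 | 3 | 7/7 = 100% (64.6–100) | 7/10 = 70% (39.7–89.2) |
| 20 | 1 | 19/19 = 100% (83.2–100) | 19/20 = 95% (76.4–99.1) |
| 20 | 2 | 18/18 = 100% (82.4–100) | 18/20 = 90% (69.9–97.2) |
| 20 | 3 | 17/17 = 100% (81.6–100) | 17/20 = 85% (64.0–94.8) |

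If one further subject is still on drug and quantifiable, n = 10 with s = 1 gives 8/9 = 88.9% against 8/10 = 80.0%. With s = 2 it gives 7/8 = 87.5% against 7/10 = 70.0%.

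**What the table would show.** Suppose two of 10 subjects are quantifiable at Week 8 and stopped, and eight are suppressed throughout. Week 8 reads 8/10 = 80% and Week 12 reads 8/8 = 100%. The percentage rises 20 points although nobody has newly responded. EOTR for the same window would be 8/10 = 80%.

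**How likely at least one stop is.** For an assumed per-subject rate q, the probability is 1 − (1 − q)^n:

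| q (assumed) | n = 10 | n = 20 |
|---|---|---|
| 2% | 18% | 33% |
| 5% | 40% | 64% |
| 10% | 65% | 88% |
| 20% | 89% | 99% |

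**The case against.** The best defence is that this is a labelled, additional, descriptive summary and that the failures are reported elsewhere. On-treatment virologic failure is a secondary endpoint in the ITT population, by arm with Wilson intervals (SAP 10.4). SAP 10.6 tabulates failures to suppress and shows breakthroughs by visit, with subject numbers. EOTR already counts missing as failure at Week 12. SVR12 does the same, so the primary result is safe. Protocol and SAP agree on the as-observed rule, and SAP 10.6 says openly that endpoints other than SVR, RVR and EOTR are shown as observed. All of this stands, and it limits the importance of the point. It does not correct the late-visit percentage or its interval. EOTR has an imputation rule but is not among the endpoints listed in SAP 10.6, and Week 10 has no counterpart that counts missing as failure.

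A reader might infer several stronger things that the documents do not support.

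- *The rate must rise at Weeks 10 and 12, or can only move toward 100%.* With no stops nothing changes. A new breakthrough lowers the observed rate, because the subject stays on drug until failure is confirmed.
- *Week 10 is affected in the same way as Week 12.* A discontinuation sample on Days 64 to 77 can enter Week 10 as quantifiable.
- *A planned comparison of Arms A and B is distorted.* Neither document plans one; efficacy is estimated arm by arm.
- *The genotype 3 results of Study M12-998 give the size.* Suppression at end of treatment there was 7 of 10 with ribavirin and 2 of 11 without. That regimen had no sofosbuvir, and these are suppression rates, not stopping rates.

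**Conclusion.** The concern holds in conditional form. If at least one subject is stopped for virologic failure, and some remaining subjects are suppressed, the as-observed percentage is too high at every later treatment visit for which the stopped subject has no admissible value. With the rest suppressed, the excess is 10 points per stop in an arm of 10 and 5 points in an arm of 20. Week 12 in the 12-week arms is the main exposure. Week 10 is exposed only when the discontinuation sample falls before Day 64. The primary analysis is not affected.

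The two Week 12 rates might be read as a contradiction. They are two stated conventions applied to one window, but the plan does not say how they relate, and a reader of the results would need to know.

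The conclusion rests on these assumptions:

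- The number of stops is assumed throughout; the documents give none.
- The protocol supplied covers Arms A and B only, so extending the point to 12-week Arms E and F assumes that the same stopping rules apply there.
- SAP 10.7 ties the virologic stopping criterion to Week 6, while Protocol 5.4.1.1 says Week 8. These passages must be reconciled, because they settle which visit is affected first.

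**What to change.** In SAP 10.6, add one rule for the by-visit percentage. A subject who has stopped study drug for virologic failure stays in the denominator and counts as not below LLOQ at every later scheduled treatment visit without an admissible value. Leave all other missing values as observed. Keep the as-observed percentage as a second row, with its n and the number stopped for virologic failure.

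A full ITT denominator would go too far. It would also fail suppressed subjects who miss a visit or stop for another reason, replacing an upward bias with a downward one.

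The same paragraph should state two relations:

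- To SAP 6.3, which counts a subject as a failure in viral response summaries after new HCV therapy starts. Read beside an as-observed rule, it could make one stopped subject a failure and drop another.
- To EOTR, so that the two Week 12 figures can be explained.

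The cost is SAP wording, one programming rule and one extra table row. Since Protocol 8.1.2.3 specifies the as-observed version, the new row should be recorded as a change from the protocol in SAP 12.1. The late-visit percentage may look slightly less favourable. No new data are needed, and the conduct of the trial does not change.

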6.3 Missing Data Imputation

No data will be imputed for any efficacy or safety analyses except for analyses of the HCV RNA endpoints.

HCV RNA values will be selected for the SVR₁₂ analysis based on defined visit windows. When there is no HCV RNA value in a visit window based on defined visit windows, the closest values before and after the window, regardless of the value chosen for the subsequent and preceding window, will be used for the flanking imputation described below.

If a subject has a missing HCV RNA value at a post-Day 1 visit, but with undetectable or unquantifiable HCV RNA levels at both the preceding value and succeeding value, the HCV RNA level will be considered undetectable or unquantifiable, respectively, at this visit for this subject. For SVR₁₂ analysis, if there is no value in the appropriate window

after flanking imputation but there is an HCV RNA value after the window, then it will be imputed into the SVR₁₂ window. Similarly, for SVR₂₄ analysis, if there is no value in the appropriate window after flanking imputation but there is HCV RNA value after the window, then it will be imputed into the SVR₂₄ window.

If a subject starts another treatment for HCV, then all HCV RNA and PRO values for this subject measured on or after the start date of the new HCV treatment will be excluded from analyses. The subject will be considered a failure for summaries of viral response at all time points after the start of the new HCV treatment.

HCV RNA < LLOQ Analyses for SVR

If a subject is missing an HCV RNA value for the visit window associated with the analysis of SVR after performing the imputations described above, then this value will be imputed with an HCV RNA value from a local laboratory if present; otherwise, the HCV RNA value for this visit will be missing. Subjects with missing HCV RNA data in the analysis window, after imputations, will be imputed as a failure.

HCV RNA Analyses for Relapse and Virologic Failure

If HCV RNA values from the central laboratory are missing but a local laboratory value is present in the appropriate time period, then the local laboratory value will be used to assess post-treatment relapse and on-treatment virologic failure.

Missing Data Imputation for PRO Questionnaires

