10.0 Efficacy Analysis

10.1 General Considerations

Analyses will be performed on the intent-to-treat (ITT) population. Sensitivity analyses of the primary endpoint, when applicable, will be performed on the mITT-GT-VF population specified in Section 5.1.1.

Missing data will be imputed as described in Section 6.3 for analyses of the HCV RNA endpoints of SVR.

Plasma HCV RNA levels will be determined for each sample collected by the central laboratory using the Roche COBAS TaqMan® real-time reverse transcriptase-PCR (RT-

PCR) assay v.2.0. For this assay, the lower limit of quantitation (LLOQ) is 25 IU/mL regardless of genotype, and the lower limit of detection (LLOD) varies by genotype. For GT3, the lower limit of detection (LLOD) is 20 IU/mL; for GT2, LLOD is 20 IU/mL. HCV RNA results that are detectable but not quantifiable are reported as "< 25 IU/mL HCV RNA detected" and those that are undetectable are reported as "HCV RNA not detected" in the database.

The notation "HCV RNA < LLOQ" is used to represent all HCV RNA values < 25 IU/mL, including values reported as "HCV RNA not detected" or "< 25 IU/mL HCV RNA detected." HCV RNA \geq LLOQ are all quantifiable values of 25 IU/mL or greater.

IL28B rs12979860 will be resulted as C/C, C/T, or T/T by the central laboratory.

Definitions for Efficacy Endpoints

Note that a confirmed quantifiable post-treatment value is defined as two consecutive post-treatment HCV RNA measurements \geq LLOQ. During treatment, a confirmed quantifiable value is defined as any two consecutive HCV RNA values \geq LLOQ, either both during treatment or at the final treatment measurement and the next consecutive post-treatment measurement.

Breakthrough = confirmed HCV RNA \geq LLOQ after HCV RNA < LLOQ during treatment, or confirmed increase from nadir in HCV RNA (two consecutive HCV RNA measurements $> 1 \log_{10}$ IU/mL above nadir) at any time point during treatment. A single breakthrough value (\geq LLOQ or $> 1 \log_{10}$ IU/mL above nadir) followed by lost to follow-up will be considered a breakthrough (i.e., will not require confirmation).

On-treatment virologic failure = breakthrough or failure to suppress during treatment (all on-treatment values of HCV RNA \geq LLOQ) with at least 6 weeks (defined as study drug duration \geq 36 days) of treatment for 12-week and 8-week treatment or at least 26 days of treatment for 6-week treatment.

RVR (rapid virologic response) = HCV RNA < LLOQ in the Week 4 window.

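### Flanking imputation for RVR and EOTR can fill an early stopper's empty treatment-period window with off-drug HCV RNA values and credit an on-treatment response

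*SAP*

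**What the plan says.** SAP 10.1 defines both endpoints by treatment-period windows. RVR is "HCV RNA < LLOQ in the Week 4 window". EOTR is "HCV RNA < LLOQ in the Week 12 window for 12-week regimen", with the Week 8 and Week 6 windows used for the shorter regimens.

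SAP 6.2 keeps off-drug data out of those windows. The notes to Tables 2, 3 and 4 each state: "Data must also have Study Drug End Day ≤ 2 for all windows".

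SAP 10.6 sends both endpoints to the Section 6.3 imputation by name, "for analyses of SVR, RVR, and EOTR where a missing response will be imputed as a failure after performing the described imputation".

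When a window has no value, Section 6.3 directs that "the closest values before and after the window, regardless of the value chosen for the subsequent and preceding window, will be used" for flanking imputation. A missing post-Day 1 visit then counts as suppressed if there are "undetectable or unquantifiable HCV RNA levels at both the preceding value and succeeding value". The only later values that Section 6.3 excludes are those on or after the start of a new HCV treatment.

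Subjects who stop early enter 48 weeks of post-treatment HCV RNA follow-up (Protocol 5.4.1, SAP 4.2), so off-drug values will usually exist.

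**The concern.** RVR and EOTR are meant to describe response while on drug. The window notes protect that meaning, but the imputation step has no matching limit. A subject who stops before the window opens necessarily has an empty window, and the nearest later value is a post-treatment one. Two subjects with the same on-drug response and the same stopping day can therefore receive different EOTR results, depending only on what happens after the last dose.

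The direction is one-way. Compared with counting such early stoppers as non-responders, the rule can only add responders, so EOTR and RVR are inflated for subjects who stop early and stay suppressed. EOTR could also disagree with the as-observed table for the same visit.

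This looks like an oversight. SAP 10.1 mentions the Section 6.3 imputation only for SVR endpoints, where bridging with post-treatment values is natural; 10.6 then extends it to RVR and EOTR without adapting it. Where the SAP does want a post-treatment value to inform an on-treatment outcome, as in confirming a quantifiable final treatment measurement (10.1), it says so.

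**Working it through.** **1. The plan's own interval.** SAP 4.3 gives 59.6–98.2% for 90% observed in 10 subjects. The Wilson limits are [p + z²/2n ± z√(p(1−p)/n + z²/4n²)] / (1 + z²/n). With p = 0.9, n = 10, z = 1.96:
- centre = (0.9 + 0.19208)/1.38416 = 0.789
- half-width = 1.96 × √(0.009 + 0.009604)/1.38416 = 0.193
- limits = 59.6% and 98.2%, which reproduces the SAP.

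**2. One subject, 12-week regimen.** The last dose is on Study Day 30 with HCV RNA below LLOQ. The Week 12 window is Days 78–98 (Table 2). Post-Treatment Weeks 2, 4, 8 and 12 fall on 30 + 14, 28, 56 and 84 = Days 44, 58, 86 and 114.
- Day 86 lies inside the window by calendar but has Study Drug End Day 56, so the note bars it and the window is empty.
- The closest values outside the window are Day 58 (End Day 28) and Day 114 (End Day 84), both off drug.
- Both below LLOQ: EOTR responder at Week 12, with no drug since Day 30.
- Day 114 quantifiable, or no later value: EOTR failure.

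**3. Other stopping days.** Samples are assumed at nominal days, with a discontinuation sample on the last-dose day. Flanks are shown as Study Day (End Day).

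| Endpoint (window) | Last dose | Preceding | Succeeding |
|---|---|---|---|
| EOTR, 12 wk (78–98) | 28 | 56 (28) | 112 (84) |
| EOTR, 12 wk | 56 | 70 (14) | 112 (56) |
| EOTR, 12 wk | 70 | 70 (0) | 126 (56) |
| EOTR, 8 wk (43–70) | 28 | 42 (14) | 84 (56) |
| EOTR, 6 wk (36–49) | 28 | 28 (0) | 56 (28) |
| RVR, 12 wk (22–42) | 21 | 21 (0) | 49 (28) |

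At every weekly stopping day that left a window empty, the succeeding flank was off drug.

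**4. The completion threshold.** A 12-week completer needs at least 77 days of drug (SAP 9.1), but the Week 12 window opens on Day 78. A completer last dosed and last sampled on Day 77 therefore has an empty window, flanked by Day 77 and Day 105 (End Day 28). This gap does not arise in the other regimens, because 49 days lies inside 43–70 and 38 days lies inside 36–49.

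**5. Size per subject.** Take all other subjects as observed responders, plus one suppressed early stopper.

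| Arm size | Early stopper not credited | Early stopper credited |
|---|---|---|
| 10 | 9/10 = 90% (59.6–98.2%) | 10/10 = 100% (72.2–100%) |
| 20 | 19/20 = 95% (76.4–99.1%) | 20/20 = 100% (83.9–100%) |

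**6. How many subjects.** Protocol Table 1 gives adverse-event discontinuation of 0.8%, 0.5%, 0.4%, 1.9% and 2.3% in active arms of 770, 401, 509, 208 and 172. That is about 6 + 2 + 2 + 4 + 4 = 18 of 2,060, or 0.9%. If that rate carried over, about 0.09 would be expected in a 10-subject arm and 0.6 in 70. Across the 0.4–2.3% range, 70 subjects give 0.3 to 1.6. Those figures come from a different regimen in genotype 1, and the documents give no rate for stops for other reasons.

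**The case against.** The strongest reply is that little depends on this. RVR and EOTR are not primary (SAP 10.3), not secondary (10.4) and not among the bulleted endpoints of 10.6. The listed on-treatment measure, unquantifiable HCV RNA at each visit, is reported as observed with no imputation. That stands, and it keeps the point minor.

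It can also be argued that a subject who has stopped has moved to the Post-Treatment Period and so has no missing Week 12 visit, and that the text does not say what to do with an off-drug sample falling on a calendar day inside the window. The second is true, but such a sample is off drug too. On the first, Section 6.3 is triggered by a window without a value and makes no exception for stoppers. Two programmers could differ, which is itself a reason to settle it.

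A reader might infer three stronger things that the documents do not support:
- **That the rule overrides missing = failure.** It does not: 10.6 assigns failure only after imputation, so failure is pre-empted in the stated order.
- **That relapse after an early stop is wrongly counted as on-treatment non-response and a correction would undo this.** A relapsing early stopper is a non-responder under the present text and under the fix below. Only those who stay suppressed at both flanks change.
- **That every off-drug flank should be barred.** For EOTR in a 12-week arm, a succeeding value after Day 98 with End Day ≤ 2 needs dosing to at least Day 97 of an 84-day regimen. A blanket limit would disable flanking even for completers who only missed the Week 12 sample, for whom a later value below LLOQ is reasonable evidence of suppression at end of treatment.

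**Conclusion.** The point holds as a minor defect. Followed literally, SAP 6.3 and 10.6 can set an early stopper's RVR or EOTR from post-treatment values that the Table 2 to 4 notes keep out of the same windows. This credits a response to early stoppers who are below LLOQ at both flanks and so inflates the two rates.

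The effect is 10 percentage points per credited subject in a 10-subject arm and 5 in a 20-subject arm. It requires a stop before the window opens (before Day 22 for RVR), no eligible value in the window, and two flanking values below LLOQ. Few subjects are likely to meet all three, with the caveat that non-adverse-event stops are not quantified. SVR12 is unaffected, because its windows are post-treatment by design. The as-observed visit table is also unaffected.

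**What to change.** Add to SAP 6.3, with a cross-reference in 10.6, a rule to this effect:

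> For RVR and EOTR, a subject whose last dose precedes the opening of the analysis window (for EOTR, one who also did not reach the completion threshold of 77, 49 or 38 days) and who has no value with Study Drug End Day ≤ 2 in that window is a non-responder. Post-treatment values are not used to fill that window.

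Keep the existing two-sided flanking rule for subjects still on drug in the window and for completers who missed the sample, including a 77-day completer last sampled on Day 77. Do not substitute the Final Treatment Visit value without a recency limit. As defined in SAP 6.1.2 it is the last value after Study Day 1, so a completer last sampled at Week 4 could become a Week 12 responder with no later confirmation.

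SAP 10.1 gives 37 days instead of 38 for the 6-week regimen in its overall-relapse definition. Both lie inside the Day 36–49 window, so this rule is unaffected, but one figure should be used.

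The cost is one or two sentences and a condition in the imputation program. EOTR may come out slightly less favourable.
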